8.3.1 Adverse event of special interest

An adverse event of special interest (AESI) is an AE (serious or nonserious) of scientific and medical concern specific to the Sponsor's product or program, for which ongoing monitoring and immediate notification by the Investigator to the Sponsor is required. Such events may require further investigation in order to characterize and understand them. Adverse events of special interest may be added, modified or removed during a study by protocol amendment.

For these AESIs, the Sponsor will be informed immediately (ie, within 24 hours), per SAE notification described [Section 8.3.2](#), even if not fulfilling a seriousness criterion, using the screens in the eCRF.

Anaphylactic reactions, systemic allergic reactions that require treatment (refer to [Section 10.15](#) for definition of anaphylaxis).

- Anaphylactic reactions, systemic allergic reactions that require treatment (refer to [Section 10.15](#) for definition of anaphylaxis).
- Severe injection site reactions (ISR) that last longer than 24 hours

Note: A severe ISR (for AE reporting) is any event that meets one of the following criteria:

- With a diameter of at least 10 cm.
- Impacting daily activities.
- With ulceration or necrosis.
- For which operative intervention is required.
- Any infection meeting at least one of the following criteria:
 - Any serious infection (SAE).
 - Requires parenteral (IV, intramuscular, SC) antimicrobial therapy
Note: Antimicrobial therapy refers to antibiotic, antiviral, and antifungal agents.
 - Requires oral antimicrobial therapy for longer than 14 days.
 - Is a parasitic infection.
 - Is an opportunistic infection (see Appendix 15: List of Opportunistic Infections, [Section 10.16](#)).
- Significant ALT elevation.
 - ALT >3 x the upper limit of normal (ULN) associated with Total Bilirubin >2 x ULN;
or
 - ALT >5 x ULN in patients with baseline ALT ≤2 x ULN; or
 - ALT >8 x ULN if baseline ALT >2 x ULN.
- Malignancy
- Pregnancy of a female patient entered in a study as well as pregnancy occurring in a female partner of a male patient entered in a study with IMP/NIMP;
 - Pregnancy occurring in a female patient entered in the clinical trial or in a female partner of a male patient entered in the clinical trial. It will be qualified as an SAE only if it fulfills one of the seriousness criteria (see Appendix 3 [[Section 10.3](#)]).
 - In the event of pregnancy in a female participant, IMP should be discontinued.

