Infections, including opportunistic infections	
Some biologic therapies have been associated with an increased risk of infection, including opportunistic infection.
 
IL-33 is a proinflammatory cytokine released by damaged epithelial cells in response to insults such as allergens, viruses, or bacteria. IL-33 signaling initiates and amplifies multiple downstream inflammatory pathways resulting in effects characteristic of both type 1 and type 2 immune inflammations. Although blockade or knockout of IL-33 signaling in mice did not reveal any unique role for IL-33 in mounting an acute immune response to viral challenge and did not lead to worsening of symptoms or outcome, patients will be monitored for signs or symptoms of infection.
 
SAR440340 inhibits the T-helper 2 (Th2) cytokines production. Infections with a diversity of helminthic parasites elicit eosinophilia via stimulation of Th2-like lymphocyte responses. The Th2 response is characterized by production of IL4, IL13, and IL5, subsequently generating IgG1 and IgE-secreting cells, and eliciting eosinophilia. Eosinophilia is prominent in a number of helminthic parasitic diseases. The eosinophilic response to helminths is determined both by the host's immune response and by the parasite, including its distribution, migration, and development within the infected host. Therefore, patients treated with SAR440340 may potentially have an increased risk of parasitic infection.
 
To minimize the risk, patients with certain type of infections are not allowed to participate in the study (eg, patients with active opportunistic or parasitic infections or at high risk of developing the infections, patients with medical history of invasive opportunistic infections, patients with HIV infection or HIV seropositivity, patients with positive screening for hepatitis B and C).
 
As a precautionary measure, the Investigator is required to carefully monitor for any signs or symptoms of infection such as, but not limited to, increased body temperature, malaise, weight loss, sweats, cough, dyspnea, pulmonary infiltrates, or serious febrile systemic illness.
 
During the study, appearance of signs or symptoms (such as abdominal pain, cough, diarrhea, fever, fatigue and hepatosplenomegaly) that could be associated with a parasitic infection should be carefully evaluated, especially if there is a history of parasitic exposure through recent travel to/or residence in endemic areas, especially when conditions are conducive to infection (eg, extended stay, rural or slum areas, lack of running water, consumption of uncooked, undercooked, or otherwise potentially contaminated food, close contact with carriers and vectors, etc). Subsequent medical assessments (eg, stool exam, blood tests, etc) must be performed in order to rule out parasitic infection/infestation.
 
Infections defined in Section 8.3.1 should be reported as AESIs with immediate notification. A complete diagnostic work-up should be performed (ie, cultures, histopathological or cytological evaluation, antigen detection and serum antibody titers). Patients should be referred to an infectious disease specialist if deemed necessary for diagnostic work up and appropriate treatment.
 
Infections or infestations that do not respond to medical treatment should have study drug discontinued until the infection is resolved.
 
For any opportunistic infection, such as TB, or other infections whose nature or course may suggest an immunocompromised status (see Section 10.16), patients must be permanently discontinued from study medication.

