9.4.2 Safety analyses

The summary of safety results will be presented by treatment group. All safety analyses will be performed on the mITT population using the following common rules:

The baseline value is defined generally as the last available value before the first dose of IMP.

Table 15 - Safety analyses

Endpoint	Statistical Analysis Methods
AE, SAE, AE leading to discontinuation	
Adverse event incidence tables will present by system organ class (SOC) (sorted by internationally agreed order), high-level group term (HLGT), high level term (HLT) and preferred term (PT) sorted in alphabetical order for each treatment group, the number (n) and percentage (%) of patients experiencing an AE. Multiple occurrences of the same event in the same patient will be counted only once in the tables within a treatment phase. The denominator for computation of percentages is the safety population within each treatment group.
 
Proportion of patients with at least one TEAE, serious TEAE, and TEAE leading to discontinuation of the study will be tabulated by treatment group. In addition TEAEs will be described according to maximum intensity and relation to the study drug. Serious AEs and AEs leading to study discontinuation that occur outside the treatment-emergent period will be summarized separately.

AESI	
The following summaries will be generated:
 
 1. Incidence of each AESI will be tabulated by treatment group. 2. The time-to-first event analyzed using K-M methods and displayed as K-M plots (cumulative incidence (%) versus time based on K-M estimates) will be provided to depict the course of onset over time. When TEAE start date or worsening date is partially available, the maximum of the earliest possible TEAE start date and the treatment start date will be used. When TEAE start date or worsening date is completely missing, the treatment start date will be used. 3. An overview summary of the number (%) of patients with 
 - any TEAE - any serious AE (regardless of treatment-emergent status) - any treatment-emergent SAE - any AE leading to death - any TEAE leading to permanent study drug discontinuation - any TEAE by maximum intensity, corrective treatment, and final outcome - cumulative incidence at specified time points (K-M estimates at Week 1, 4, 12, 24, 52 and 72) 
Definitions of AESIs and the method to identify AESIs will be specified in the SAP.

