Injection site reactions (serious/severe and lasting 24 hours or longer)	
HLT = 'Injection site reaction' and either with serious status or non-serious events with (AE end date/time-AE start date/time) ≥ 24 hours or ongoing and at least one of the following checked on the Injection Site Reaction Complementary Form:
 
 - Diameter of at least 10cm - Prevents daily activities - Presence of ulceration or necrosis - Operative intervention required
Infection	
Primary SOC = 'Infections and infestations' and meeting at least one of the following criteria
 
 - Serious status - 'Have any parental treatment (IV, Intramuscular, SC) been given for this event?' is answered Yes on eCRF Infection Event Form - 'Did this event require Prolonged Medication (greater than 14 Days)?' is answered Yes on eCRF Infection Event Form
Parasitic infection	Infection Type 'Parasitic' selected on eCRF Infection Event Form
Opportunistic infection	'Has the AE been assessed as opportunistic infection?' is answered Yes on eCRF Infection Event Form
Potential drug-related hepatic disorder	Drug-related hepatic disorders-Comprehensive search narrow SMQ (20000006)
Malignancy	Sub-SMQ (20000091)-Malignant or unspecified tumors
Pregnancy	'Pregnancy' or 'Partner Pregnancy' ticked on the Pregnancy eCRF.
Symptomatic overdose with IMP	'Overdose of IMP' and 'Symptomatic Overdose' are both ticked Yes on the Overdose eCRF
Symptomatic overdose with NIMP	'Overdose of NIMP' and 'Symptomatic Overdose' are both ticked Yes on the Overdose eCRF
Other selected AE grouping	
Injection site reaction	HLT = 'Injection site reaction'

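### The SAP's infection AESI rule omits the protocol's antimicrobial restriction, so it can count non-serious infections that the protocol does not define as AESIs

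*SAP*

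**What the plan says.** Protocol 8.3.1 lists the ways an infection becomes an AESI: it is serious, parasitic or opportunistic, or it meets one of two treatment criteria. The first is "Requires parenteral (IV, intramuscular, SC) antimicrobial therapy". The second is "Requires oral antimicrobial therapy for longer than 14 days". A note fixes the drug class: "Note: Antimicrobial therapy refers to antibiotic, antiviral, and antifungal agents". Table 6 of the same section tells sites to use this definition: "Infections defined in Section 8.3.1 should be reported as AESIs with immediate notification".

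SAP Table 4 (2.1.4.1) builds its infection category from "Primary SOC = 'Infections and infestations' and meeting at least one of the following criteria". The criteria are serious status, a Yes to "Have any parental treatment (IV, Intramuscular, SC) been given for this event" (presumably a slip for parenteral), or a Yes to "Did this event require Prolonged Medication (greater than 14 Days". Both questions come from the eCRF Infection Event Form. Parasitic and opportunistic infections have their own rows.

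The AESI outputs in SAP 2.4.5.1 are driven by these search criteria. SAP 1.5, which lists changes to the protocol's statistical section, mentions only the high-eosinophil population and the SGRQ responder endpoint.

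**The concern.** The drug-class restriction is missing from both treatment criteria in the SAP, and the oral restriction is missing from the second. As written, a non-serious infection can enter the AESI tables because it was given something other than an antimicrobial.

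Protocol 2.3 names infection as a potential risk of blocking this pathway, so this is one of the safety categories readers will look at first. A category that mixes clinically significant infections with infections given prolonged supportive or topical treatment is harder to interpret. Extra background events in both arms pull the risk ratio towards 1. The count may also differ from the AESIs that sites report within 24 hours under the protocol definition, with nothing in the SAP to explain the gap.

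**Working it through.** The check is mainly a comparison of text; there is no planned figure to reproduce.

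| Criterion | Protocol 8.3.1 | SAP Table 4 |
|---|---|---|
| Serious | Yes | Yes |
| Parenteral | Antimicrobial only | Any treatment |
| Over 14 days | Oral antimicrobial only | Any medication the event required |
| Parasitic, opportunistic | Yes | Yes, separate rows |
| Medical review | Not applicable | None for infection; stated for anaphylaxis and hypersensitivity |

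**Does the SAP rule miss protocol cases?** Among events coded to the infections system organ class, no. Parenteral antimicrobial therapy is a parenteral treatment, and an oral antimicrobial needed for more than 14 days is prolonged medication. Every event meeting a protocol treatment criterion should therefore be answered Yes.

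**Does the SAP rule admit others?** As worded, yes. A non-serious infection given intravenous fluids but no parenteral antimicrobial meets the SAP rule only. So does one that required an intranasal corticosteroid or antihistamine for more than 14 days (both are permitted by protocol 6.5), or a skin infection needing a topical antifungal for that long, which fails the protocol on route.

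**How wide is the opening?** Three provisions narrow it.
- Protocol 8.1.1.1 and 8.3.7 keep COPD exacerbations out of adverse event reporting unless serious.
- Protocol 6.5 prohibits systemic steroids except for exacerbations, apart from one course of up to 6 days in 24 weeks for other reasons.
- Protocol Appendix 3 makes hospitalisation, generally including an overnight emergency-ward stay, a seriousness criterion. Much intravenous supportive care would therefore qualify under both rules.

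**What would an excess do?** The documents give no infection rates, so this shows direction only. Assume protocol-defined infection AESIs in 5% of placebo and 10% of SAR440340 patients, with *x* points of extra patients added to each arm.

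| *x* | Rates | Ratio | Difference |
|---|---|---|---|
| 0 | 10% v 5% | 10/5 = 2.00 | 5 points |
| 1 | 11% v 6% | 11/6 = 1.83 | 5 points |
| 3 | 13% v 8% | 13/8 = 1.63 | 5 points |
| 6 | 16% v 11% | 16/11 = 1.45 | 5 points |

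The ratio shrinks and the difference does not. The difference becomes less precise. With 170 per arm, its standard error is √(0.10×0.90/170 + 0.05×0.95/170) = 2.8 points at *x* = 0, and √(0.13×0.87/170 + 0.08×0.92/170) = 3.3 points at *x* = 3. No value of *x* is supported by the documents, and the provisions above argue against the higher ones.

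**The case against.** **The form is not in the documents.** The two SAP criteria are question labels, and they follow the protocol's own structure: the same three routes and the same 14-day cut. The form or its completion guidance may restrict them to antimicrobials. This stands. A reader might infer that the table will count events outside the protocol definition; the documents support only that it can.

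**The SAP was given this job.** Protocol 9.4.2 says: "Definitions of AESIs and the method to identify AESIs will be specified in the SAP". Other Table 4 rows also differ from the site-reporting criteria; the hepatic row is a MedDRA query where the protocol uses ALT thresholds. So a reader should not infer that the SAP lacked authority, and neither document promises that the tables will reconcile with the 24-hour reports. But protocol 8.3.1 fixes the infection criteria and says AESIs are modified by protocol amendment. A wider rule, if intended, should be declared.

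**No signal is hidden.** A reader might infer that true infection AESIs are lost or a real risk difference is diluted. Neither follows: the SAP set contains the protocol set, and equal additions leave the difference unchanged. The analysis is descriptive, and the AESI summaries also show preferred term, seriousness, corrective treatment and outcome. This limits the consequence but does not remove the mismatch.

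**A derived drug rule could do harm.** SAP 2.5.3 does not impute medication dates, and no direct link between event and medication is described beyond the recorded reason for use. Replacing the site's answers with a programmed rule could drop true cases. This stands and shapes the fix.

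**Conclusion.** The mismatch holds on the wording. For non-serious infections, SAP Table 4 is wider than protocol 8.3.1 on both treatment criteria, has no review step to narrow it, and is not declared in SAP 1.5.

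The number of extra events cannot be estimated from the documents. It could be nil if the form already restricts the questions, and the rules on exacerbations, systemic steroids and seriousness suggest it may be small. Efficacy analyses are untouched. The point is worth correcting because infection is a named risk and the remedy is cheap. The conclusion assumes that the eCRF questions mean what their labels say and that qualifying infections are coded to the infections system organ class.

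**What to change.** Keep the two eCRF answers in SAP Table 4 as the search step. Then add a blinded medical review, as the anaphylaxis and hypersensitivity rows already have. It should confirm from the coded concomitant medications (WHO-DD coding in SAP 2.1.2, ATC classes in 2.4.2) that the parenteral treatment was an antibiotic, antiviral or antifungal, or that such a drug was needed orally for longer than 14 days.

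Retain as an AESI any event whose drug link or duration cannot be determined, so that no true case is lost to incomplete dates. Leave the serious, parasitic and opportunistic criteria as they are, and correct the spelling of parenteral.

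Tabulate the protocol-defined infection AESIs. If the wider set is also wanted, show it as a separate row and declare it in SAP 1.5. If the form's guidance already restricts both questions to antimicrobials, Table 4 should say so.

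The cost is a SAP wording change, a small amount of programming to list candidate events with their medications, and a short blinded review before unblinding. No new data are collected.

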Elevated liver function tests	
No preclinical and clinical data has suggested any hepatic toxicity of SAR440340; however, as a general consideration of clinical development, the administration of immunosuppressant or immunomodulating agents may represent an additional risk factor for hepatotoxicity.
 
In order to closely follow liver function tests (LFT), assessment of total protein, albumin, total bilirubin (in case of values above the normal range, differentiation in conjugated and nonconjugated bilirubin), alanine aminotransferase, aspartate aminotransferase, and alkaline phosphatase are measured as part of the clinical laboratory testing.
 
Guidance for the investigation of elevated LFTs as well as concurrent management of IMP is provided in Section 10.6.

	ALT elevations defined in Section 8.3.1 should be reported as AESIs with immediate notification.
Malignancy	In toxicology studies on SAR440340-mediated IL-33 blockade, the effect of SAR440340 administration has not demonstrated the development of malignancy. Long term use has not been studied. The investigator should carefully monitor for any signs or symptoms of malignancy. Malignancy should be reported as AESI with immediate notification.
Pregnancy	In case of positive urinary test, the study treatment will be withheld and a serum pregnancy test should be performed as soon as possible to confirm the pregnancy. Pregnancy will lead to definitive treatment discontinuation in all cases. Refer to Section 1.3 for the schedule of pregnancy tests performed throughout this study.

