8.3.2 Time period and frequency for collecting AE and SAE information

All AEs and SAEs will be collected from the signing of the ICF up to the end of study visit at the time points specified in the SoA ([Section 1.3](#)), or up to recovery or stabilization of any AE to be followed-up as specified in this protocol, whichever comes last.

All SAEs and AESI will be recorded and reported to the Sponsor or designee within 24 hours, as indicated in Appendix 3 ([Section 10.3](#)). The Investigator will submit any updated SAE and AESI data to the Sponsor within 24 hours of it being available.

Investigators are not obligated to actively seek AE or SAE after conclusion of the study participation. However, if the Investigator learns of any SAE, including a death, at any time after a participant has been discharged from the study, and he/she considers the event to be reasonably related to the IMP or study participation, the Investigator must promptly notify the Sponsor.

The method of recording, evaluating, and assessing causality of AE and SAE and the procedures for completing and transmitting SAE reports are provided in Appendix 3 ([Section 10.3](#)).

Adverse event (SAE and AESI) reporting is summarized in [Table 7](#).

Table 7 – Adverse event reporting

Adverse event/laboratory abnormality	Reporting timeframe
Serious adverse event	Within 24 hours
Pregnancy	Within 24 hours
Overdose	Symptomatic Asymptomatic
	Routine
ALT elevation	
	ALT >3 x ULN and associated with total bilirubin >2 x ULN
	Within 24 hours
	ALT >5 ULN if baseline ALT is ≤2 ULN
	Within 24 hours
	ALT >8 ULN if baseline ALT is >2 ULN
	Within 24 hours
Anaphylactic or systemic allergic reactions that require treatment.	Within 24 hours

Adverse event/laboratory abnormality	Reporting timeframe
Severe injection site reactions that last longer than 24 hours.	Within 24 hours
Infections as defined in Table 6	Within 24 hours
Malignancy	Within 24 hours

ALT: alanine aminotransaminase; ULN: upper limit of normal.

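### SAP Table 4 finds the hepatic AESI by a coded-term search, so the protocol's three-threshold ALT event is not tabulated as defined

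*SAP*

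**What the plan says.** **Protocol.** Section 8.3.1 makes significant ALT elevation an AESI if any one of three conditions is met:

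1. "ALT >3 x the upper limit of normal (ULN) associated with Total Bilirubin >2 x ULN"
2. "ALT >5 x ULN in patients with baseline ALT ≤2 x ULN; or"
3. "ALT >8 x ULN if baseline ALT >2 x ULN"

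Table 7 in section 8.3.2 repeats the three for 24-hour reporting, for example "ALT >8 ULN if baseline ALT is >2 ULN". Table 6 refers back to them: "ALT elevations defined in Section 8.3.1 should be reported as AESIs with immediate notification". Section 7.1.1 uses the same cut-offs among the criteria for permanent discontinuation of an individual patient. Table 15 in section 9.4.2 commits to tabulating the incidence of each AESI by treatment group.

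Two protocol statements say where an AESI definition comes from. Section 8.3.1 says "Adverse events of special interest may be added, modified or removed during a study by protocol amendment". Section 9.4.2 says "Definitions of AESIs and the method to identify AESIs will be specified in the SAP".

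**SAP.** Table 4 (section 2.1.4.1) has one hepatic AESI, labelled as a potential drug-related hepatic disorder, and its whole criterion is "Drug-related hepatic disorders-Comprehensive search narrow SMQ (20000006". Section 2.4.5.1 builds the AESI summary from the Table 4 searches. Section 1.5 lists two changes from the protocol, the high-eosinophil population and the SGRQ responder endpoint, and neither concerns AESIs.

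**The concern.** The protocol's hepatic AESI is a laboratory event judged partly against the patient's own baseline. The SAP's hepatic AESI is a group of coded terms. A term search reads no laboratory value, so membership depends on whether an investigator reported an event and how it was coded.

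This can go wrong in two directions. A rise below the protocol thresholds can enter the row if it was reported as an adverse event under a hepatic term. A value above a threshold stays out if no adverse event with a matching term was recorded.

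What is at stake is safety reporting and traceability. The hepatic AESI count by arm would not reconcile with the ALT events that sites must report within 24 hours, or with discontinuations made on the same cut-offs in protocol 7.1.1.

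The contrast within Table 4 is also telling. Injection site reactions, overdose and most infection criteria keep the protocol's qualifiers (duration, severity, route, symptoms). The liver row does not.

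**Working it through.** No figure in the plan needs reproducing. The check asks whether any planned SAP output returns the count that protocol 8.3.1 defines.

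**Inputs**
- Protocol thresholds 1 to 3: section 8.3.1, as quoted above.
- SAP AESI row: Table 4, term search only.
- SAP laboratory rows (potentially clinically significant abnormalities, PCSA): Appendix A gives cumulative ALT bands of >3, >5, >10 and >20 x ULN, and a combined row of ALT >3 with total bilirubin >2 x ULN. Section 2.4.5.3 counts them by arm over the treatment-emergent period, using scheduled and unscheduled, central and local results.
- Baseline split in those tables: normal or missing versus abnormal by PCSA criterion. For ALT the lowest criterion is >3 x ULN.
- Screening limit: E37 excludes ALT above 3 x ULN at Visit 1.

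**Constructed cases** (values in multiples of ULN; bilirubin normal unless stated)

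| Baseline ALT | Post-dose value | Protocol AESI? | SAP AESI row | SAP laboratory rows |
|---|---|---|---|---|
| 1 | ALT 6 | Yes (2) | Only through a coded term | >5 |
| 2.5 | ALT 9 | Yes (3) | Only through a coded term | >5 |
| 2.5 | ALT 6 | No | Possible if reported | >5 |
| 1 | ALT 4 | No | Possible if reported | >3 |
| 1 | ALT 4, bilirubin 2.5 | Yes (1) | Only through a coded term | Combined row |

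The second and third patients fall in the same laboratory row, but only one is a protocol AESI. Nothing in the planned tables separates them.

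**What the laboratory rows can bound.** Let P be the number of patients meeting the protocol definition on laboratory values, A the combined row, B5 the ALT >5 row and B10 the ALT >10 row. Take baseline ALT as known.
- 10 exceeds both 5 and 8, so every B10 patient qualifies whatever the baseline: P ≥ B10.
- Thresholds 2 and 3 both imply ALT >5, and threshold 1 implies membership of A: P ≤ A + B5.

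Within B5, the patients who do not qualify under threshold 2 or 3 are exactly those with baseline above 2 and a peak above 5 but not above 8. They are protocol AESIs only if they meet threshold 1.

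The combined row uses threshold 1's cut-offs but pairs ALT and bilirubin within a treatment phase regardless of the interval between them. The protocol asks for the two to be associated. The row could therefore be slightly wider than threshold 1.

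**Result.** Threshold 1 is recoverable subject to the pairing rule. Thresholds 2 and 3 are contained in one row but cannot be isolated there. No planned table gives the three-part event.

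**The case against.** The strongest reply is that the protocol hands this to the SAP. Section 9.4.2 delegates AESI definitions as well as the method of finding them, so the SAP may be acting within its remit. The amendment rule in 8.3.1 can be read as governing what sites monitor and notify, which the SAP leaves alone. That has force. It makes this a tension between two protocol statements that should be reconciled, not a plain breach. For the same reason, the silence of SAP 1.5 counts for little: that section concerns the protocol's statistical section, and the ALT thresholds sit in section 8.

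A reader might infer that the protocol's ALT events go uncounted. The documents do not support that. Sites must report them as AESIs, all adverse events are coded and tabulated, and such an event enters the SAP row whenever its term belongs to the search. The term list is not in the documents, so they show neither capture nor loss. Nor are the events absent by arm: the combined row and the ALT >5 row show them, and SAP 2.4.5.3 adds flagged listings, a possible Hy's law listing and a plot of peak ALT against peak bilirubin.

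A reader might also infer that any small rise becomes an AESI. It does not. Protocol 10.3 makes a laboratory abnormality an adverse event only if the investigator considers it clinically significant. Nor do the thresholds form a study stopping rule. In 7.1.1 they are criteria for individual patients, and protocol 9.5 and SAP section 3 both say that no formal stopping rules apply.

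What survives is that delegation does not remove the mismatch between the event sites report and the event the AESI row counts, and that the laboratory tables bound the protocol count without giving it.

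**Conclusion.** The SAP's hepatic AESI row counts a different set of patients from the protocol's hepatic AESI, and the three-part protocol event is not tabulated as defined. The claim goes no further than that. It does not say that threshold events are lost.

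The number of patients affected cannot be derived from the documents. For the ALT >5 row, the ambiguity is confined to patients with baseline ALT above 2 x ULN. That group is probably small, because E37 removes anyone above 3 x ULN at screening. Baseline is the last value before first dose, so a baseline somewhat above 3 remains possible. For the term-search row, the discrepancy in either direction depends on investigators' reporting and coding, which cannot be known in advance.

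The effect is on safety reporting and traceability. Efficacy, alpha and power are unaffected.

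**What to change.** In SAP Table 4, add an AESI row for significant ALT elevation, derived from laboratory values in the treatment-emergent period with the three protocol thresholds and each patient's baseline ALT. State how ALT and bilirubin values are paired for threshold 1. Reconcile the derived cases with the ALT events that sites reported as AESIs, and list any that appear in only one source.

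Move the hepatic term search to the table's additional AE groupings. The SAP already does this for injection site reactions, where the qualified event is the AESI and the unqualified term search is listed separately.

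Add a sentence reconciling the amendment rule in protocol 8.3.1 with the delegation in 9.4.2. If the sponsor prefers to keep the term search as the AESI, the SAP should say so, give the reason, and note that the row does not count the protocol's event.

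The cost is one derived flag, one table row and a reconciliation listing, all from data already collected. No site procedure or clinical rule changes.
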